3.6.3.2 Current status of Follicular Lymphoma

The following current status of FL information will be summarised and listed:

- Time since most recent relapse (months), calculated as:

12[date of informed consent - date of most recent relapse before Betalutin treatment + 1]/365.25, reported to 1 decimal place*

- Current subtype diagnosis: grade I-IIIa or other
- Whether B symptoms present at current visit: No, Yes.

3.6.3.3 Previous treatment for Follicular Lymphoma

The following previous treatment for Follicular Lymphoma information will be summarised and listed:

- Number of prior systemic therapies (derived by excluding radiotherapy and regimen number 99, which corresponds to previous LYMRIT-37-01 PART B exposure to rituximab for any participants re-enrolled, and then counting the distinct regimen numbers. If a regimen contains a mixture of treatments including radiotherapy then radiotherapy and systemic therapy will have the same numbering and the regimen number covering this “composite” regimen should be included).
- Participants with 2 or more prior systemic therapies: No, Yes
- Has the participant exhausted all previous lines of therapy? No, Yes.
- Whether received prior rituximab/anti-CD20 No, Yes determined following clinical review of unique WHO Drug coding *.
- Time from last treatment for FL to first study drug administration (months), calculated as:

12 [date of first study drug administration (i.e. rituximab) – date of last course of last treatment for FL prior to date of informed consent + 1]/365.25*

If partial dates are reported for last course of last treatment, the 15th will be used when day is missing and 1st July when day and month are missing.

- Response to last treatment for FL (Complete remission, Partial Remission, Stable disease (No change), Progressive disease, Unknown, Not applicable). Where last treatment for FL is defined as last treatment for FL prior to date of informed consent.
- Last therapy refractory (yes/no).
- Refractory to 2 or more prior therapies for FL (No, Yes).
- Refractory to rituximab/anti-CD20 (No, Yes).

* A clinical review of the unique coded WHO drug terms will be conducted by the sponsor to set the regimes into individual components (rituximab/anti-CD20).

Part C:

Initial diagnosis, current status and previous treatments for iNHL will be summarised using a similar approach to that for FL.

3.6.4 Prior Medications

Prior medications will be coded according to the World Health Organization Drug dictionary (WHO Drug) (Standard) version utilised for the survival follow-up to date reporting of PART A. The version used will be indicated in the listings. No summaries are required.

Prior medications are those with a start and stop date prior to the first administration of rituximab.

3.6.5 Administration of Study Treatment and Exposure

Administration of Study Treatment and Exposure will be summarised by dose regimen of the actual treatment received.

3.6.5.1 Betalutin

The investigational product, Betalutin, is injected on the nominal Day 0 visit (Study day 1). The weight, actual volume injected (mL) and the total radioactivity injected over all injections (converted to MBq/kg body weight (b.w.) i.e. standardising for body weight) and weight (kg) will be summarised.

Total radioactivity injected over all injections will be derived as follows:

Total radioactivity injected over all injections (MBq/kg b.w.) = $\sum_{i=1}^n \left(\frac{[RA]_{i^p} - [RA]_{i^a} + [RA]_{i^f}}{b.w.} \right)$

where,

n = number of injections (1 or 2)

$[RA]_{i^p}$ = radioactivity in injection i prior to administration

$[RA]_{i^a}$ = radioactivity in injection i after administration

$[RA]_{i^f}$ = radioactivity in filter for injection i after administration (if applicable)

b.w. = body weight as recorded on the Betalutin administration eCRF page

Details relating to administration of the investigational product, including whether Betalutin was administered within 4 hours of lilotomab administration and radioactivity in syringe prior to injection, after injection and in the filter after injection MBq will be listed.

Percentage of prescribed dose will be determined programmatically as follows:

$$\left[\frac{\text{Total radioactivity injected (MBq/kg.b.w.)} - \text{Dose (MBq/kg.b.w.)}}{\text{Dose (MBq/kg.b.w.)}} \right] \times 100$$

Differences of +/- 10% of prescribed dose will be flagged, determined programmatically where percentage of prescribed dose > 10% or < -10%.

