The syringe should be shielded from β radiation during preparation and administration of the patient doses. Aseptic technique should be used in the administration of Betalutin. Each patient will receive one dose in accordance with the treatment schedule. Betalutin will be given as a slow bolus injection using a shielded syringe driver. After administration, the syringe and line must be flushed with a minimum of 10 mL of sterile normal saline (0.9% NaCl) after injection, as detailed in the Drug Handling Plan. The equipment used in connection with the preparation and administration of the study medication, are to be treated as radioactive waste and should be disposed in accordance with hospital procedure for handling of radioactive material.

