9.5 Treatment Compliance

Patients will receive Betalutin treatment under supervision of a nuclear medicine specialist (or any other specialist physician authorised to administer radiopharmaceuticals per local regulations). Study centre personnel will check the administration volume and total radioactivity injected and will record the activity dose and volume injected in the patient’s source documents and eCRF.

Patients will receive infusions of lilotomab and rituximab under surveillance by trained

personnel used to handle infusions with rituximab. The volume to be given will be prepared by the pharmacy following instructions of the drug handling manual and the infusion bags will be delivered as ready to use solutions.

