Lilotomab infusion within 4 hours before Betalutin administration	Dose (assigned and actual), start and end time of infusion, batch number and pre-medication needs to be recorded. Record pulse rate, blood pressure and body temperature pre-infusion, 15 min, 30 min, 45 min, 1 hour after infusion start and 30 minutes and 1 hour post-infusion
(S)AE	Any (S)AE after lilotomab infusion should be recorded
Day 0 – Betalutin administration	
Betalutin injection	Patient weight, assigned dose level, volume injected, batch number, time of injection and radioactivity in syringe prior and after injection need to be recorded
Day 0 - Post dose procedures and assessments	
Vital signs	2 hours post-dose: blood pressure, body temperature
(S)AE	Any (S)AE after Betalutin administration should be recorded
Concomitant medication	Any medication given post-Betalutin should be recorded

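### As printed, the SAP adds filter residue to the activity injected; any non-zero filter reading then overstates MBq/kg, so check the sign on the original page and in the program

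*SAP*

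**What the plan says.** SAP 3.6.5.1 defines total radioactivity injected, in MBq per kg body weight, as a sum over injections ("n = number of injections (1 or 2"). The numerator for each injection is "RA]_{i^p} - [RA]_{i^a} + [RA]_{i^f". Superscript p is the activity before administration and a the activity after it. Superscript f is defined as "radioactivity in filter for injection i after administration (if applicable".

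The same section treats the filter as a reading of its own: "radioactivity in syringe prior to injection, after injection and in the filter after injection MBq will be listed". The derived total is then compared with the prescribed dose as a percentage deviation, and "Differences of +/- 10% of prescribed dose will be flagged".

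The protocol mentions no filter. Section 9.6.2.1 asks that "radioactivity in syringe prior and after injection need to be recorded". Section 9.1.4 describes a shielded syringe driver, after which "the syringe and line must be flushed with a minimum of 10 mL of sterile normal saline". Under section 9.5, site staff check the total "radioactivity injected and will record the activity dose and volume injected".

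**The concern.** Activity measured in a filter after administration stayed behind, so it is a loss in the same sense as syringe residue. The printed formula subtracts one loss and adds the other. Neither document gives a reason for the plus sign.

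The bias runs one way: a non-zero filter reading can only raise the derived value. It can therefore pull a true under-delivery back inside the lower 10% limit, or push a patient who is inside the upper limit beyond it. Exposure is one of the few categories this abbreviated SAP still analyses formally (Table 1), and the limits match the dose tolerance in Protocol 9.1.1 and 9.1.4. The primary and secondary efficacy endpoints, the analysis sets and the investigator's dosing-error reports (Protocol 16.3.6) do not use this derivation.

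**Working it through.** **Inputs.** The formula and definitions come from SAP 3.6.5.1. The regimens used for illustration, 15 and 20 MBq/kg, come from SAP Table 4. Neither document gives a syringe or filter reading, so every filter share below is an assumption. There is no published figure to reproduce.

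**Step 1: mass balance per injection**, with body weight w.

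- Printed: (p − a + f) / w.
- If *after* is the syringe alone, delivered activity is (p − a − f) / w. The printed form exceeds it by 2f / w.
- If *after* already includes the filter, delivered activity is (p − a) / w. The printed form exceeds it by f / w.

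The separate listing of the two post-injection readings supports the first case. Both differences are positive for any f > 0 and zero when f = 0. With two injections, the excesses add.

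**Step 2: size.** Let F be the filter activity as a percentage of prescribed dose, and k = 2 or 1 for the two cases. The excess is k × F percentage points, or k × F/100 × dose in MBq/kg.

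Example: 70 kg at 15 MBq/kg is 1050 MBq. F = 1% is 10.5 MBq, and 2 × 10.5 / 70 = 0.30 MBq/kg.

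| Assumed F | Excess, points (k = 2 / k = 1) | At 15 MBq/kg (k = 2 / k = 1) | At 20 MBq/kg (k = 2 / k = 1) |
|---|---|---|---|
| 0% | 0 / 0 | 0 / 0 | 0 / 0 |
| 1% | 2 / 1 | 0.30 / 0.15 | 0.40 / 0.20 |
| 3% | 6 / 3 | 0.90 / 0.45 | 1.20 / 0.60 |
| 5% | 10 / 5 | 1.50 / 0.75 | 2.00 / 1.00 |

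**Step 3: effect on the flag.** The rule flags a deviation above +10% or below −10%. If the true deviation is T, the printed formula reports T + kF.

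- T = 0: falsely flagged when kF > 10, so F > 5% (k = 2) or F > 10% (k = 1).
- T = −11%: goes unflagged once −11 + kF ≥ −10, so from F = 0.5% (k = 2) or 1% (k = 1).
- T = +9%: falsely flagged when 9 + kF > 10, so F > 0.5% (k = 2) or F > 1% (k = 1).

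**Step 4: two cases built from assumed readings**, as a percentage of prescribed dose, with *after* as syringe only.

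- p = 100, a = 3, f = 8. Printed: 100 − 3 + 8 = 105, or +5%, no flag. Filter subtracted: 100 − 3 − 8 = 89, or −11%, flagged.
- p = 107, a = 2, f = 6. Printed: 107 − 2 + 6 = 111, or +11%, flagged. Filter subtracted: 107 − 2 − 6 = 99, or −1%, no flag.

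**The case against.** The strongest objection is that the plan itself may be right. The finding rests on one sign in an equation read from PDF text, and the intended p − (a + f) becomes exactly the printed string if one inner bracket is lost. The nested superscripts already suggest imperfect conversion. This stands as a reason to look at the page before calling it an error. It does not show that a bracket was lost: the outer parentheses of the same formula and the brackets of the percentage formula in that section both survived.

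A second objection is that the filter's position is not described. If the filter's activity were counted in the after reading but had never been in the prior reading (for example, retained when the syringe was filled), then p − (a − f) = p − a + f would be correct. The documents do not strictly exclude this, but nothing in the SAP supports it: the term is defined as a reading after administration and is listed apart from the syringe.

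Third, the consequence is small, and this stands. The protocol names no filter, the SAP term applies only where relevant, and the flag changes only if the excess carries a patient across a 10% limit. The study was terminated early and the exposure summary is descriptive. Because the component readings are listed, a reader can recompute the value.

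**Conclusion.** Wrong as written, and minor. On the SAP's own definitions the printed formula adds undelivered activity to the activity injected. It overstates the result by 2f / w per injection if the after reading excludes the filter, or by f / w if it includes it. The direction is certain under either reading. The size is not, because no filter readings are given, and the number of affected patients may be zero. The conclusion also depends on the plus sign being on the original page. Only the page and the exposure program can settle that, so confidence that the plan or the code is actually wrong is moderate.

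**What to change.** 1. Check the sign and any inner bracket on the original SAP page, and check what the exposure program computes.
2. Establish whether the after reading is the syringe alone, and state it in the SAP.
3. If the sign is as printed and the after reading is syringe only, write the numerator as p − (a + f) for each injection, with f set to 0 when no filter was used. If the after reading already contains the filter, use p − a, so that the filter is not subtracted twice.
4. Compare the derived totals with the activity dose recorded by the site under Protocol 9.5. Rerun the exposure summary and the 10% flag if any value changes.

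The cost is one formula line and one derivation check. The syringe and filter readings are already to be listed and the site's activity dose is already in the eCRF, so no new data are needed. If the original page shows the bracket, it is enough to confirm that the program matches it.

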3.6.5.2 Rituximab

Participants are pre-dosed with 375 mg/m² rituximab once on Day -14. The actual rituximab dose administered (mg) and the actual dose standardised by BSA (mg/m²), as well as weight and BSA at rituximab infusion, will be summarised.

$$\text{Rituximab dose administered (mg/m}^2\text{)} = \text{Rituximab dose (mg)/BSA (m}^2\text{)}$$

Details relating to administration of rituximab will be listed separately.

3.6.5.3 Lilotomab

Lilotomab will be infused within 4 hours prior to Betalutin administration. The total lilotomab dose (mg) and dose standardised by body weight (kg), as well as body weight (kg) and BSA (mg/m²) at lilotomab infusion will be summarised.

$$\text{Standardised lilotomab dose administered (mg/kg b.w.)} = \text{Lilotomab dose (mg)/b.w. (kg)}$$

$$\text{Standardised lilotomab dose administered (mg/m}^2\text{)} = \text{Lilotomab dose (mg)/BSA (m}^2\text{)}$$

Details relating to administration of lilotomab will also be listed separately.

3.7 Efficacy Analyses

All efficacy analyses will be based on the Efficacy analysis set which includes patients with FL on the following dose regimens: “40/15” and “100/20”.

The evaluation of tumour response will be based on the assessment made by the IRC, based on the standard criteria [Cheson 2014]. The disease response (RS) dataset will be transferred from ICON to Veristat according to the data delivery specification and will contain responses per visit per subject per assessor. In cases where more than one independent assessor (e.g. RADIOLOGIST 1, RADIOLOGIST 2) provide independent assessments at the same time point the flag variable RSACPTFL=”Y” identifies the record that is considered to be the accepted assessment. Best overall response will be used for the ORR and CRR endpoints. DoR and DoCR will be derived from the visit responses.

All data relating to the efficacy endpoints detailed below, including derived variables, will be listed for all patients who had data from an IRC assessment.

For calculation purposes, incomplete dates will be imputed as 1st of the month when day is missing and 1st January when day and month are missing.

3.7.1 Primary Endpoint: Overall Response Rate (ORR) as assessed by IRC assessment

3.7.1.1 Definition of Overall Response Rate (ORR)

A response of CR, PR, Stable Disease (SD), Progressive Disease (PD) and Not Evaluable (NE) is allowed. The response definitions for each category are based on standard criteria and defined in Section 12.3 of the protocol.

If disease assessments for a participant are not available then the response rate for the relevant timepoint will be set to Not Done (ND).

The Overall Response Rate (ORR) is defined as the proportion of participants who achieve a best response of CR or PR at any time. If all disease assessments for a participant are not available then ORR will be set to NE.

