5.6 Study Endpoints Part B: FL phase IIb

Efficacy endpoints definitions are provided in [Section 14.1.7](#).

Primary endpoint:

- ORR as assessed by an independent reviewer based on standard criteria [Cheson 2014] (40)

Secondary endpoints:

Efficacy endpoints:

- ORR by investigator assessment
- CRR by independent review and investigator assessment
- DoR and DoCR by independent review and investigator assessment
- PFS by independent review and investigator assessment
- OS
- Change from baseline in the sum of the product of the greatest perpendicular diameters (SPD) of target lymph nodes as documented radiographically.

Safety endpoints:

Incidence and severity of AEs.

Exploratory endpoints:

- Changes in QoL as reported by patients using the FACT-Lym questionnaire (Version 4).
- Pharmacokinetic assessments e.g. total lilotomab antibodies measurements in serum (total lilotomab antibodies pharmacokinetics) and total radioactivity measurements in blood (Betalutin pharmacokinetics).

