14.1.2.3 Part B – Population treated with “40/15” Regimen

Note - At the interim analysis, the SRC decided to discontinue the “100/20” treatment regimen, and continue with further recruitment in the “40/15” treatment regimen only.

A total of 87 patients, including the those from the interim analysis, will be recruited and treated with the “40/15” regimen.

With 87 patients, there will be more than 90% power to detect a difference of 18% in response rates using a two-sided exact test with a target significance level of 0.05, assuming the response rate under the null hypothesis is 30% and the response rate under the alternative hypothesis is 48%. If there are at least 36 responders in 87 patients, then there will be at least 97.5% chance that the true response rate will be at least 30%.

Moreover, with 87 patients, there will also be more than 90% power to detect a difference in complete response rate of 8% under the null hypothesis versus 20% under the alternative hypothesis.

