14.1.5 Statistical Methods

Results from Part A (Phase I and Phase IIa), Part B and Part C will be summarised separately due to differences in study design, dose regimens and patient populations. However, analyses in specific populations and for specific dose regimens may be performed in the overall study population.

The results from this study will be presented mostly using descriptive statistical methods. Details of planned analyses for Parts A, B and C will be provided in separate statistical analysis plans.

All statistical programming and analyses will be performed using SAS[®] software.

Data will generally be presented by time of measurement. In general, continuous variables will be described using standard summary statistics such as number of observations, mean value, standard deviation, minimum value, maximum value, median, and first and third quartiles. Categorical variables will be summarised in frequency tables as count and percentages.

All individual data collected in the eCRF will be presented in data listings. Patients screened but not included in the study will not be presented in any tables or listings.

Prior to database lock and analysis of the final study data, a detailed Statistical Analysis Plan (SAP) will be prepared and approved, describing all the analyses to be performed. The SAP will document any changes to the analyses described in this protocol.

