14.1.7 Analysis of Efficacy Data

Tumour response will be reported as follows in individual patients:

- CR
- PR
- SD
- PD
- NE

In Part A and Part C: Response rate will be presented as a point estimate of the proportion of responders along with the 95 % exact confidence interval of response rate.

In Part B randomised period: The ORR will be compared between dosing regimens using the Fisher's Exact test, and the difference in response rates and the corresponding 95% exact CI will be presented. ORR estimates and 95% exact CI for each dosing regimen will also be presented.

In Part B Single-arm 40/15 part: – The primary efficacy analysis on ORR (based on independent assessment) will be performed by testing whether the ORR is less than or equal to 30% against the alternative hypothesis that ORR is greater than 20% at overall two-sided 5% level of significance, i.e.,

$H_0: p = 0.3$ vs. $H_a: p \neq 0.3$

In addition, the secondary efficacy analysis on CRR (based on independent assessment) will be performed by testing whether the CRR is less than or equal to 8% against the alternative hypothesis that ORR is greater than 8% at overall two-sided 5% level of significance, i.e.,

H0: $p = 0.08$ vs. Ha: $p \neq 0.08$

Responders are defined as having CR and PR according to definition in [Section 12.3](#).

Time to event endpoints will be analysed using standard Kaplan-Meier techniques. The estimate of the median survival curve will be calculated along with the associated 95% confidence intervals (when applicable). The efficacy endpoints are:

Overall Response Rate (ORR)

ORR, defined as the proportion of patients who achieve a CR or PR assessed with the use of standard criteria for lymphoma (1). The ORR will be assessed at 3 months image evaluation.

Best ORR will also be evaluated, taking the best response achieved independent of time point for image evaluation.

Complete Response Rate (CRR)

CRR, defined as the proportion of patients who achieve a CR assessed with the use of standard criteria for lymphoma (1). The CRR will be calculated based on complete responses achieved at any timepoint.

Progression-free survival (PFS)

PFS is defined as the interval from Betalutin administration and date of:

- Relapse (new or enlarged lesions after CR).
- Progression (new or enlarged lesions after PR or SD).
- Death from any cause.

If none of the above events are observed, PFS will be censored at the date of the last adequate tumour assessment

Duration of response (DoR)

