3.10 Changes from the Protocol Planned Analysis

There are considerable changes from planned protocol analysis as the study was terminated early and an abbreviated CSR and SAP produced. This SAP covers only the outputs required from Veristat for reporting. The abbreviated CSR will include information from other sources, ie the results of the interim analysis. This will be documented in the CSR.

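### The SAP makes best response at any time the primary ORR, specifies no summary of the protocol's 3-month ORR, and does not name the change

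*SAP*

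**What the plan says.** **Protocol.** Section 5.6 lists IRC-assessed ORR as the Part B primary endpoint without a timepoint and refers onward: "Efficacy endpoints definitions are provided in" Section 14.1.7. That section says "The ORR will be assessed at 3 months image evaluation" and then "Best ORR will also be evaluated, taking the best response achieved independent of time point for image evaluation". It sets CRR, by contrast, at any timepoint. Section 14.1.5 adds: "The SAP will document any changes to the analyses described in this protocol".

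**SAP.** Section 3.7 bases both ORR and CRR on best overall response. Section 3.7.1.1, under the primary endpoint heading, reads: "The Overall Response Rate (ORR) is defined as the proportion of participants who achieve a best response of CR or PR at any time". Section 3.7.1.2 then plans response counts and a Clopper-Pearson interval for ORR regardless of time, and nothing for Month 3. On departures from the protocol, Section 3.10 says "There are considerable changes from planned protocol analysis as the study was terminated early". It does not mention the ORR definition.

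**The concern.** The protocol treats the 3-month rate as the endpoint and best response as an extra. The SAP promotes the extra and specifies no summary of the original. Because the protocol gives CRR a different timing in the same section, the 3-month timepoint for ORR does not read as loose wording.

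Three things are at stake:

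- **Direction.** In the same patients, the any-time rate can only equal or exceed the 3-month rate.
- **Unequal opportunity.** After early termination, the last patients dosed may have one post-treatment scan while early patients have several. An any-time rate mixes these; a fixed timepoint does not.
- **Disclosure.** The SAP Introduction describes in the past tense a July 2022 review of patients with IRC-read baseline and 3-month scans. The definition therefore stands in a plan written after 3-month results had been reviewed. Nothing in the documents shows that results drove the change, but this is a reason to name it.

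**Working it through.** **1. The protocol's design figure.** Section 14.1.2.3 plans 87 patients, "assuming the response rate under the null hypothesis is 30"% and 48% under the alternative, with a two-sided exact 5% test and power above 90%. With X binomial:

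- P(X ≥ 35 | n = 87, p = 0.30) = 0.0269, above 0.025
- P(X ≥ 36 | n = 87, p = 0.30) = 0.0157, so the critical count is 36
- P(X ≥ 36 | n = 87, p = 0.48) = 0.911

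This reproduces both the stated power and the protocol's benchmark, "If there are at least 36 responders in 87 patients". Restoring the 3-month endpoint changes none of these figures.

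**2. Direction.** Let a be the number with IRC CR or PR at Month 3, b the number whose only CR or PR falls at another assessment, and n the efficacy set. The 3-month ORR is a/n and the any-time ORR is (a + b)/n, with b ≥ 0.

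**3. Size per late responder.** The documents do not give n for 40/15. I assume a range from 61 (patients in the July 2022 review) to 86 (just under the target of 87).

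- Shift in ORR: 100/61 = 1.64 points; 100/86 = 1.16 points.
- Shift in the exact lower limit, starting from rates of about 30% to 48%: 1.4 to 1.5 points (n = 61); 1.0 to 1.1 points (n = 86).

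The Clopper-Pearson lower limit is the 2.5% quantile of Beta(x, n − x + 1). The upper limit is the 97.5% quantile of Beta(x + 1, n − x).

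| Responders | ORR | Exact 95% CI |
|---|---|---|
| 25/61 | 41.0% | 28.55–54.32% |
| 26/61 | 42.6% | 30.04–55.94% |
| 34/86 | 39.5% | 29.15–50.66% |
| 35/86 | 40.7% | 30.22–51.83% |
| 35/87 | 40.2% | 29.85–51.29% |
| 36/87 | 41.4% | 30.92–52.45% |

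These counts are hypothetical and chosen at the boundary. One late responder carries the lower limit past 30% only when the Month 3 count sits exactly there.

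**4. Illustration at the design size.** Suppose the true 3-month ORR is 30% and a share f of Month 3 non-responders responds later. The documents give no f, so a range is shown. The any-time ORR is 0.30 + 0.70f.

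| f | Any-time ORR | P(≥ 36 of 87) |
|---|---|---|
| 0 | 30.0% | 0.016 |
| 2% | 31.4% | 0.031 |
| 5% | 33.5% | 0.076 |
| 10% | 37.0% | 0.230 |
| 15% | 40.5% | 0.474 |

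No such test is planned in the SAP. The table shows only why the two rates should not be read against the same 30%.

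**5. Could early termination explain the change?** No. The SAP Introduction plans at least 3 months of follow-up after the last 40/15 patient in Part B is dosed, and Section 3.7 says the IRC dataset holds responses by visit. The 3-month rate remains feasible.

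**The case against.** The best case for the SAP has several parts.

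- **Best ORR is itself in the protocol.** True: the SAP promoted a planned measure and did not invent one. The synopsis and Section 14.1.2.2 also follow the primary endpoint with a scan schedule running to 60 months, and Section 14.2 schedules ORR at more than one analysis. None of this overrides the definition in Section 14.1.7. The amendment summary drops presentation at each timepoint but leaves the 3-month definition in the current text.
- **The planning rates carry no timepoint.** Section 14.1.2.3 says only response rate, so linking 30%/48% to Month 3 is an inference. It is a strong one, because Section 14.1.7 tests ORR against 30% in the same section that defines ORR at 3 months.
- **A 3-month result may reach the report another way.** SAP Section 3.10 says the CSR will include interim results, and the July 2022 review used 3-month scans. That would cover only 61 patients selected for having both scans. Visit-level IRC data will also be listed, so the rate should be recoverable, but without a planned estimate, interval or missing-scan rule.
- **By-visit output may have been intended.** Not Done is defined for a timepoint yet appears in the any-time list. The TFL shells are not available, and the SAP text specifies no such output.
- **The report is descriptive.** This stands. The SAP plans no test, says the study is not powered for its original objectives, and follows a decision to terminate. It limits the consequence but does not remove the discrepancy.

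**Conclusion.** The concern holds. The primary ORR specified in the SAP is not the protocol's primary ORR, the protocol's measure has no specified summary, and the change is not named where the protocol says it should be. The direction is certain given the same patients and denominator. The size is not known: the number of first responses after Month 3 may be zero, and the per-responder shifts rest on an assumed efficacy set of 61 to 86. No formal type I error is affected. What is affected is the headline estimate, its interval and how both compare with the design rates. It should be fixed, in proportion to a descriptive close-out report.

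**What to change.** - In SAP Sections 3.7.1.1 and 3.7.1.2, define primary ORR as IRC CR or PR at the Month 3 assessment, over all patients in the Efficacy Analysis Set for the regimen, with the Clopper-Pearson interval.
- State that patients without an evaluable Month 3 assessment count as non-responders. Neither document says this in so many words, but it follows from the protocol's ITT percentage denominator. It needs stating because the default in SAP Section 3.1 bases percentages on non-missing observations and does not list efficacy among its exceptions.
- State the scan window. Protocol Section 6.3 allows 7 days either side for imaging; the Days 78 to 122 window in SAP Section 3.3 is written for laboratory and change-from-baseline outputs.
- Keep any-time best ORR, with its exact interval, as the supportive measure that matches the any-time CRR and the DoR responders.
- Name any remaining departure in SAP Section 3.10.

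The cost is SAP wording and one extra table from the per-visit IRC responses already due to be transferred. The headline ORR may be lower, and primary-ORR responders may be fewer than the patients in the DoR analysis, which needs a table footnote. If any-time ORR is kept as primary, the least that is needed is a sentence in Section 3.10 saying so and a 3-month table beside it.
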